## **12 REGULATORY CONSIDERATIONS**

### **12.1 Institutional Review Board/Ethics Committee Approval**

The protocol for this study has been designed in accordance with the general ethical principles outlined in the Declaration of Helsinki. The review of this protocol by the IRB/EC and the performance of all aspects of the study, including the methods used for obtaining informed consent, must also be in accordance with principles enunciated in the declaration, as well as ICH Guidelines, Title 21 of the Code of Federal Regulations (CFR), Part 50 Protection of Human Subjects and Part 56 Institutional Review Boards.

The Investigator will be responsible for preparing documents for submission to the relevant IRB/EC and obtaining written approval for this study. The approval will be obtained prior to the initiation of the study. The approval for both the protocol and informed consent must specify the date of approval, protocol number and version, or amendment number.

Any amendments to the protocol after receipt of IRB/EC approval must be submitted by the Investigator to the IRB/EC for approval. The Investigator is also responsible for notifying the IRB/EC of any serious deviations from the protocol, or anything else that may involve added risk to subjects.

Any advertisements used to recruit subjects for the study must be reviewed and approved by the IRB/EC prior to use.

### **12.2 Informed Consent**

The Investigator must obtain informed consent of a subject or his/her designee prior to any study related procedures as per GCPs as set forth in the CFR and ICH guidelines.

Documentation that informed consent occurred prior to the subject's entry into the study and the informed consent process should be recorded in the subject's source documents. The original consent form signed and dated by the subject and by the person consenting the subject prior to the subject's entry into the study must be maintained in the Investigator's study files.

### **12.3 Subject Confidentiality**

In compliance with United States federal regulations, Karyopharm requires the Investigator to permit its representatives and, when necessary, representatives of the FDA or other regulatory authorities to review and/or copy any medical records relevant to the study in accordance with local laws.

Should direct access to medical records require a waiver or authorization separate from the subject's statement of informed consent, it is the responsibility of the Investigator to obtain such permission in writing from the appropriate individual.

### **12.4 Study Record Requirements**

The Investigator must ensure that the records and documents pertaining to the conduct of the study and the distribution of the study drug, that is copies of CRFs and source documents (original documents, data, and records [e.g., hospital records; clinical and office charts; laboratory notes; memoranda; subject's diaries or evaluation checklists; SAE reports, pharmacy dispensing records; recorded data from automated instruments; copies or transcriptions certified after verification as being accurate copies; microfiches photographic negatives, microfilm, or magnetic media; x-rays; subject files; and records kept at the pharmacy, at the laboratories, and at medico-technical departments involved in

the clinical study; documents regarding subject treatment and study drug accountability; original signed informed consents, etc.]) be retained by the Investigator for as long as needed to comply with national and international regulations (generally 2 years after discontinuing clinical development or after the last marketing approval). The Investigator agrees to adhere to the document/records retention procedures by signing the protocol.

### **12.5 Premature Discontinuation of the Study**

The responsible local clinical Investigator as well as Karyopharm has the right to discontinue this study at any time for reasonable medical or administrative reasons. Possible reasons for termination of the study could be but are not limited to:

- Unsatisfactory enrollment with respect to quantity or quality.
- Inaccurate or incomplete data collection.
- Falsification of records.
- Failure to adhere to the study protocol.

## **13 REGULATORY AND REPORTING REQUIREMENTS**

### **13.1 Adverse Events**

**(All serious adverse events (SAE) must be reported to Karyopharm within 24 hours of the investigational staff's knowledge; this includes any event that occurs during the participation of the trial regardless of associated therapy, severity or relationship)**

**Adverse events which occur during screening and before the initiation of the treatment phase of the trial will not be captured / reported as they are not related to treatment.**

### **13.2 Serious Adverse Event (SAE) Definition**

A serious adverse event is one that at any dose (including overdose):

- Results in death
- Is life-threatening
- Requires inpatient hospitalization or prolongation of existing hospitalization
- Results in persistent or significant disability or incapacity
- Is a congenital anomaly or birth defect
- Is an important medical event
- Suspected positive pregnancy

“Life-threatening” means that the subject was at immediate risk of death at the time of the serious adverse event; it does not refer to a serious adverse event that hypothetically might have caused death if it were more severe.

“Persistent or significant disability or incapacity” means that there is a substantial disruption of a person’s ability to carry out normal life functions.

Medical and scientific judgment should be exercised in deciding whether expedited reporting is appropriate in situations where none of the outcomes listed above occurred. Important medical events that may not be immediately life-threatening or result in death or hospitalization but may jeopardize the patient or may require intervention to prevent one of the other outcomes listed in the definition above should also usually be considered serious. Examples of such events include allergic bronchospasm requiring intensive

treatment in an emergency room or at home, blood dyscrasias or convulsions that do not result in inpatient hospitalization, or the development of drug dependency or drug abuse. A new diagnosis of cancer during the course of a treatment should be considered as medically important. Severe Adverse Events which occur during screening and before the start of study therapy will not be collected and reported.

### **13.3 Adverse Drug Reporting**

Toxicity will be scored using CTCAE Version 4.03 for toxicity and adverse event reporting. A copy of the CTCAE Version 4.0 can be downloaded from the CTEP homepage (<http://ctep.info.nih.gov>). All appropriate treatment areas should have access to a copy of the CTCAE Version 4.0. All adverse clinical experiences, whether observed by the investigator or reported by the patient, must be recorded, with details about the duration and intensity of each episode, the action taken with respect to the test drug, and the patient's outcome. The investigator must evaluate each adverse experience for its relationship to the test drug and for its seriousness. Note that only adverse events that are greater than grade 1 will be captured in the case report forms and reported.

The investigator must appraise all abnormal laboratory results for their clinical significance. If any abnormal laboratory result is considered clinically significant, the investigator must provide details about the action taken with respect to the test drug and about the patient's outcome.

Moffitt Cancer Center and all participating sites will report SAEs by completing an SAE report in ONCORE, the electronic data capture system. The SAE must be reported by email ([[contact]](mailto:[contact])) to the MCRN within 2 working days.

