## LIST OF ABBREVIATIONS AND DEFINITIONS OF TERMS

AE	Adverse event
ALT (SGPT)	Alanine aminotransferase
AML	Acute myeloid leukemia
ANC	Absolute neutrophil count
AST (SGOT)	Aspartate aminotransferase
AUC	Area under the curve
BMI	Body mass index
BSA	Body surface area
BUN	Blood urea nitrogen
CBC	Complete blood count
CHF	Congestive heart failure
CI	Confidence interval
CNS	Central nervous system
CR	Complete response
CRF	Case report form
CRM1	Chromosome region maintenance protein 1
CTCAE	Common terminology criteria for adverse events
CT Scan	Computed Tomography Scan
CYP450	Cytochrom P450
D	Day
DLT	Dose-limiting toxicity
DNA	Deoxyribonucleic acid
ECG	Electrocardiogram
ECOG	Eastern Cooperative Oncology Group
EOT	End of treatment
GCP	Good Clinical Practice
GI	Gastrointestinal
GLP	Good laboratory practice
H	Hour
HFS	Hand foot syndrome
HR	Hazard ratio
ICH	International Conference on Harmonization
IMWG	International myeloma working group
INR	International normalized ratio
IRB	Institutional review board
ITT	Intent to treat
IV	Intravenous
LDH	Lactate dehydrogenase
m 	Square metre (body surface area)
Mg	Milligram
Min	Minute
MyPRS	Myeloma Prognostic Risk Signature
MCRN	Moffitt Clinical Research Network
MI	Milliliter
MRI	Magnetic resonance imaging
MTD	Maximum tolerated dose

NCI	National Cancer Institute
NES	Nuclear export signal
NYHA	New York Heart Association
ORR	Overall response rate
OS	Overall survival
PD	Pharmacodynamics
PFS	Progression-free survival
PK	Pharmacokinetics
LD	liposomal Doxorubicin
PO	Per oral
PR	Partial response
PTT	Partial thromboplastin time
RP2D	Recommended phase II dose
Topo II	Topoisomerase II
SAE	Serious adverse event
SD	Stable disease
SINE	Selective inhibitor of nuclear export
SUSAR	Suspected unexpected serious adverse reaction
TSH	Thyroid stimulating hormone
TSP	Tumor suppressor protein
TTP	Time to progression
UNL	Upper normal limit
WBC	White blood cell count
XPO1	Exportin 1

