#### 11.4 Study Design

The phase I portion of the trial will be a standard “3+3” design. The details of this design are listed as follows.

Number of patients with DLT	Escalation Decision Rules
0/3	Enter 3 patients at the next higher dose level.
≥2	Dose will be de-escalated to the prior lower dose level. Three additional patients will be enrolled to that lower dose cohort unless 6 patients had been treated at that lower dose. If ≤1 of 6 patients experience DLT, then this lower dose will be declared the MTD.
1/3	Enter 3 more patients at this dose level. If 0 of 3 patients experience DLT, proceed to the next higher dose level. If ≥1 patient suffers DLT, then dose will be de-escalated to the previous lower level. Three additional patients will be enrolled to that lower dose cohort unless 6 patients had been treated at that lower dose. If ≤1 of 6 patients experience DLT, this lower dose level will be declared the MTD.
≤1 out of 6 at highest dose level	This is the MTD/recommended phase II dose. At least 6 patients must be entered at the MTD/recommended phase II dose.

Four dose level escalations of oral selinexor / LD are planned. The number of patients needed for the determination of the MTD can thus vary from 6 to 24 patients. For Phase 1 MTD Portion, dose limiting toxicities (DLTs) will be summarized at the conclusion of each dose level, and reviewed by the investigators and the Protocol Monitoring Committee and

the decision to proceed to the next dose level will be made accordingly. The MTD is defined as the highest dose that causes one or less patients out of 6 to have a DLT.

The phase II portion is a single-arm Simon optimum two stage design.

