Participating study sites should NOT report SAEs to the FDA. Rather, participating sites should report SAEs to Karyopharm Therapeutics and H. Lee Moffitt Cancer center, and H. Lee Moffitt Cancer center will be responsible for reporting to FDA.

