**13.5.2 Reporting to karyopharm**

In addition to reporting to the FDA, Sponsor-Investigator will forward completed SAE and pregnancy forms to representatives of karyopharm. Forms will be completed and emailed to [REDACTED]

Address and Phone Number of person/sponsor responsible for SAE management

[REDACTED]  
[REDACTED]  
[REDACTED]  
[REDACTED]

IN ADDITION, scanned form must be emailed to the following recipients:

[REDACTED]  
[REDACTED]  
[REDACTED]

The Sponsor / investigator is responsible for providing 6-month Adverse Reaction Reports (all AEs assessed as causality related to Karyopharm investigational product) to Karyopharm [REDACTED] throughout the duration of the study. These reports are to contain listings of non-serious (expected or unexpected) adverse reactions and serious or non-serious expected adverse reactions which were collected during the 6-month report cycle

*The Sponsor is responsible for obtaining any additional follow-up information regarding safety reports, upon request from Karyopharm.*

*Karyopharm will inform the Sponsor regarding any SUSAR detected in other clinical studies, ISTs, or Compassionate Use as promptly as possible upon becoming aware of same*

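### Sites have 24 hours to report an SAE to the drug supplier but 2 working days to notify the network of the institution that reports to FDA, so the sponsor side can learn after the supplier

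*Combined protocol and SAP*

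**What the plan says.** Section 13.1 (Adverse Events): all SAEs, whatever their relationship to treatment, "must be reported to Karyopharm within 24 hours of the investigational staff's knowledge".

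Section 13.3 (Adverse Drug Reporting): "Moffitt Cancer Center and all participating sites will report SAEs by completing an SAE report in ONCORE", and the SAE must be emailed "to the MCRN within 2 working days". The section gives no starting point for the 2 working days and no deadline for the ONCORE entry. The list of abbreviations expands MCRN as "Moffitt Clinical Research Network", so it belongs to the lead center.

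Section 13.5.1 (Reporting to FDA): participating sites are told not to report to FDA. They report to the supplier and the lead center, and "H. Lee Moffitt Cancer center will be responsible for reporting to FDA". The same section assigns the forwarding of SAEs to the Sponsor-Investigator. For unexpected fatal or life-threatening events it sets an outer limit of 7 calendar days, counted from the sponsor's first receipt. It also contains a sentence that has every participating physician-investigator report certain reactions to FDA, which does not fit the instruction that sites must not.

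Section 13.5.2 (Reporting to karyopharm): the "Sponsor-Investigator will forward completed SAE and pregnancy forms to representatives of karyopharm", with no deadline in that sentence.

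Section 3.1 describes the study as investigator-sponsored and names three centers. The supplier is therefore not the sponsor, and two of the centers are external.

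**The concern.** The shorter deadline goes to the supplier, and the longer one to the organization that carries the sponsor's duty to FDA. A site can meet both limits and still leave the sponsor side uninformed for days after the supplier had to be told. Because the FDA period begins at the sponsor's receipt, any delay before that receipt is added to the total time from the event becoming known to FDA hearing of it.

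The routes are also hard to turn into one procedure. Sections 13.1 and 13.5.1 have the site report directly to the supplier. Section 13.5.2 has the Sponsor-Investigator forward the forms. A site that reads the forwarding as a substitute for its own report, and uses its full 2 working days, can miss the supplier's 24 hours.

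What is at stake is timely safety oversight and a reporting procedure that sites can follow. The primary endpoint, the sample size and the analysis are unaffected.

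**Working it through.** The plan states no figure to reproduce. The check sets the deadlines side by side and converts working days to calendar days.

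Inputs:
- Limit for the supplier: 24 hours = 1 day from staff knowledge (Section 13.1).
- Limit for the MCRN email: 2 working days, start not stated (Section 13.3).
- FDA limit for unexpected fatal or life-threatening events: 7 calendar days from the sponsor's receipt (Section 13.5.1).

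Assumptions, because the plan defines none of these: working days are Monday to Friday; the period starts on the day the site becomes aware; that day is not counted; and receipt by the MCRN counts as receipt by the sponsor.

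Formulas:
- Excess over the supplier's limit = calendar days to MCRN − 1.
- Latest FDA notice, in days after site awareness = calendar days to MCRN + 7.

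| Day of awareness | Email due | Calendar days | Excess over supplier's limit | Latest FDA notice |
|---|---|---|---|---|
| Monday | Wednesday | 2 | 2 − 1 = 1 | 2 + 7 = day 9 |
| Tuesday | Thursday | 2 | 1 | day 9 |
| Wednesday | Friday | 2 | 1 | day 9 |
| Thursday | Monday | 4 | 4 − 1 = 3 | 4 + 7 = day 11 |
| Friday | Tuesday | 4 | 3 | day 11 |
| Saturday | Tuesday | 3 | 3 − 1 = 2 | 3 + 7 = day 10 |
| Sunday | Tuesday | 2 | 1 | day 9 |

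If the MCRN had the supplier's limit, the latest FDA notice would be 1 + 7 = day 8 whatever the weekday. The present wording therefore moves the ceiling from day 8 to between day 9 and day 11. If the following Monday is a holiday, Thursday or Friday awareness gives 5 calendar days: 5 − 1 = 4 days beyond the supplier's limit, and 5 + 7 = day 12.

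Other channels to the lead center:
- ONCORE: Section 14.3.3 identifies it as the lead center's own database, so an entry there may be seen before the email. Section 13.3 sets no deadline for the entry, so earlier sight is possible but not required.
- Study calls: Section 14.3.2 has them weekly in phase I and monthly in phase II. A monthly call cannot close a gap of 1 to 3 days.

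The MCRN email is thus the only site-to-lead-center report with a stated deadline.

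**The case against.** The strongest reply is that these are ceilings. Sites may report sooner, Section 13.5.1 asks for notice to FDA as soon as possible, and the 7-day limit can still be met as written. Day 11 arises only with Thursday or Friday awareness; from Monday to Wednesday the shift is one day. All of this stands, and it keeps the size modest. It does not remove the mismatch, since the written limits still allow the gap.

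It can also be said that Sections 13.5.1 and 13.5.2 are compatible: the site reports to the supplier and the Sponsor-Investigator forwards forms as well. That is right. The two routes are an unreconciled duplication, not a strict contradiction.

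The 2-working-day rule binds the lead center as well as the other sites. The delay to the sponsor matters mainly for events at the two external centers.

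A reader might infer three stronger points that the documents do not support:
- That the MCRN decides dose levels, so that escalation could go ahead uninformed. Section 11.4 has DLTs "reviewed by the investigators and the Protocol Monitoring Committee" at the end of each dose level, and Section 14.2 describes that committee as independent. Section 1.5.2 already names dose level 2m as the recommended phase II dose, so escalation is largely moot.
- That the sponsor hears last of all. ONCORE may show the event earlier, and FDA hears after the sponsor in any case.
- That patients would be registered who otherwise would not be. The MCRN does register patients (Section 4.3). At the accrual in Section 3.2, 3 patients per 5 weeks, the largest excess of 3 days covers (3/35) × 3 = 0.26 registrations across all sites. No rule was identified that pauses registration after a single SAE, so earlier notice would not by itself prevent them.

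**Conclusion.** The concern holds as a mismatch of deadlines with a consequence for FDA timing. For an SAE at an external site, the sponsor side can be told 1 to 3 calendar days after the supplier's 24-hour limit with every written deadline met. For an unexpected fatal or life-threatening event, the latest compliant FDA notice is then day 9 to 11 after site awareness, where a common 24-hour limit would give day 8.

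The figures rest on the working-day convention stated above and on the MCRN email being the sponsor's first receipt. An earlier look at ONCORE would shorten the gap; a holiday would lengthen it by a day for Thursday-to-Sunday awareness. The point is modest in size and worth correcting because the remedy is cheap. It supports no claim about dose escalation or about a number of patients exposed.

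**What to change.** In Section 13.3, replace the 2-working-day limit with the limit and starting point already in Section 13.1, 24 hours from the time the site's study staff know of the event. Apply it to both the ONCORE entry and the MCRN email.

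In Section 13.5, set out one route. The site sends the same SAE form to the MCRN and the supplier at the same time. State in Section 13.5.2 that the Sponsor-Investigator's forwarding is for follow-up information and does not replace the site's own report. Align the sentence in Section 13.5.1 that has each physician-investigator report to FDA with the later instruction that participating sites do not.

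The cost is a few sentences in Sections 13.3, 13.5.1 and 13.5.2. Sites already owe the supplier a report within 24 hours, so the added work is one more recipient and a prompt ONCORE entry. The downside is less slack for sites at weekends.

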### **13.4 Karyopharm Drug Safety Contact information**

### **13.5 Investigator Reporting Responsibilities**

#### **13.5.1 Reporting to FDA**

The conduct of the study will comply with all FDA safety reporting requirements. IND Annual Reports

If the FDA has granted an IND number, it is a requirement of 21 CFR 312.33, that an annual report is provided to the FDA within 60-days of the IND anniversary date. 21 CFR 312.33 provides the data elements that are to be submitted in the report

Serious adverse events will be forwarded to FDA by the Sponsor-Investigator according to 21 CFR 312.32.

It is the responsibility of the PI and the research team to ensure serious adverse events are reported according to the Code of Federal Regulations, Good Clinical Practices, the protocol guidelines, the sponsor's guidelines, and Institutional Review Board policy.

All adverse experience reports must include the patient number, age, sex, weight, severity of reaction (mild, moderate, severe), relationship to study drug (probably related, unknown relationship, definitely not related), date and time of administration of test medications and all concomitant medications, and medical treatment provided. The investigator is responsible for evaluating all adverse events to determine whether criteria for "serious" and as defined above are present.

Adverse drug reactions that are Serious, Unlisted/unexpected, and at least possibly associated to the drug, and that have not previously been reported in the Investigators brochure, or reference safety information document should be reported promptly to the Food and Drug Administration (FDA) in writing by each investigator/physician engaged in clinical research. A clear description of the suspected reaction should be provided along with an assessment as to whether the event is drug or disease related.

The investigator/physician shall notify the FDA by telephone or by fax of any unexpected fatal or life threatening experience associated with the use of the drug. As soon as possible, but no later than 7 calendar days after the sponsors initial receipt of the information. Each phone call or fax shall be transmitted to the FDA new drug review division in the Center for Drug Evaluation and Research or the product review division in the Center for Biologics Evaluation and Research that has responsibility for review of the IND if applicable.

Participating study sites should NOT report SAEs to the FDA. Rather, participating sites should report SAEs to Karyopharm Therapeutics and H. Lee Moffitt Cancer center, and H. Lee Moffitt Cancer center will be responsible for reporting to FDA.

